## 1.2.3 Preclinical Information

Refer to the asapiprant IB for a detailed preclinical (nonclinical) information and safety profile.

## 1.2.4 Clinical Information

Refer to the asapiprant IB for detailed Clinical Information.

## 1.3 Risk/Benefit and Ethical Assessment

Refer to the asapiprant IB for information on the Risk/Benefit and Ethical Assessment.

## 1.4 Compliance Statement

[figure not shown]
This study will be conducted in accordance with this protocol, the International Council for Harmonisation of Technical Requirements for Pharmaceuticals for Human Use Guideline for Good Clinical Practice E6 (ICH GCP, 1996; E6 R2, 2017), Title 21 of the United States Code of Federal Regulations (US CFR), the European Union (EU) Directives (2001/20/EC; 2005/28/EC), and applicable national and local regulatory requirements. The responsibilities of BioAge Labs and Investigator(s) are described fully in Appendices 2.2 and 2.3, respectively.

## 2 STUDY RATIONALE, OBJECTIVES AND ENDPOINTS

### 2.1 Rationale for the Study

The effect of asapiprant treatment on SARS-CoV infection was evaluated in female 8-month old C57BL/6 mice that had been infected intranasally with mouse-adapted SARS-CoV. Mice were monitored daily for weight loss (morbidity) and mortality for up to 14 days. Asapiprant (30 mg/kg) was administered by oral gavage (PO) to fed mice once daily starting in the morning of Day 2 post infection and ending on the morning of Day 5 post infection (4 administrations). Two independent treatment studies were performed. Treatment with asapiprant was associated with a significantly reduced body weight loss as compared to control groups. As shown in [Figure 1](#), untreated mice rapidly lost body weight after infection. Six of the 7 mice in the study shown were euthanized in the vehicle group for reaching the humane endpoint of  $\geq 25\%$  body weight loss. In contrast, when treatment with asapiprant started on Day 2, body weight loss stopped and reversed, and all 7 treated mice survived the infection. Therefore, once daily treatment with 30 mg/kg asapiprant for 4 days starting 2 days after infection effectively stopped weight loss (morbidity) and completely prevented mortality in a lethal mouse model of SARS-CoV. In a satellite group of 3 animals each, asapiprant-treatment was associated with an 84% reduction of lung virus titers at Day 5 after infection as compared to the vehicle control group.

**Figure 1: Mortality and Body Weight Change in SARS-CoV Infected Mice**

[figure not shown]

Once daily oral treatment with 30 mg/kg asapiprant for 4 days starting 2 days after infection. Mortality: log-rank (Mantel-Cox) Test; vehicle (n=7) vs asapiprant (n=7); p value = 0.0012. Source: Report BRR175001IVVP20

This clinical study will evaluate the PGD2-DP1 axis as a therapeutic target for severe COVID-19. This target is simultaneously dysregulated by immune aging and in COVID-19 patients. Therefore, inhibition of the PGD2-DP1 axis is expected to therapeutically benefit all COVID-19 patients, but most specifically older patients, who have the highest morbidity and mortality in this disease, and hence the highest unmet medical need. Modulation of this target can simultaneously boost the antiviral immune response against SARS-CoV-2 infection (mediated

by dendritic and NK cells) while also reducing the nonspecific tissue damage caused by infiltration of neutrophils into the lungs of infected patients (Figure 2) (Jandl et al., 2016).

**Figure 2: Investigational Product Asapiprant Inhibits PGD2 Signaling via the DP1 Receptor to Potentially Treat COVID-19**

Abbreviations: CCR7 = C-C motif chemokine receptor 7; COVID-19 = coronavirus disease 2019; DC = dendritic cell; DP1 = prostaglandin D2 receptor 1; IFN- $\gamma$  = interferon gamma; NK cell = natural killer cell; PGD2-DP1 signaling = the therapeutic target of the investigational drug BGE-175 to treat COVID-19; RTIs = respiratory tract infections

Consequences of DP1 inhibition include improved dendritic cell migration and NK-cell function (and thus a boost in the adaptive immune response), plus reduced neutrophil infiltration, thus reducing immune-mediated tissue damage. “Cohorts” refers to BioAge Labs longitudinal human cohort data where molecular profiling of blood samples have linked specific mechanisms to the aging process, future longevity, and healthspan in aging individuals.

## 2.2 Study Objectives

To evaluate the efficacy of asapiprant given by PO or nasogastric tube (NG) administration versus placebo on the clinical signs and symptoms of COVID-19 infection in hospitalized subjects  $\geq$  50 years of age.

### 2.2.1 Secondary Objectives

- To evaluate the ability of asapiprant given by PO or NG administration to accelerate the clearance of the COVID-19 virus in subjects with symptomatic disease requiring hospitalization
- To determine the efficacy of asapiprant by demonstrating improvement in COVID-19 illness and prevention of progression to respiratory failure (RF) using various endpoints
- To evaluate the safety profile of asapiprant given by PO or NG administration in subjects  $\geq$  50 years of age hospitalized with COVID-19 infection

## 2.2.2 Other Objectives

- To investigate the effect of asapiprant on inflammation markers of COVID-19 infection, including but not limited to interleukin (IL)-6, C-reactive protein (CRP), IL-10, tumor necrosis factor alpha (TNF- $\alpha$ ), IFN- $\gamma$ , interferon alpha (IFN- $\alpha$ ), IFN- $\gamma$ -induced protein 10 (IP-10), monocyte chemoattractant protein-1 (MCP-1), cluster of differentiation (CD)4+ and CD8+ T cells, and absolute lymphocyte count
- Determine peak and trough concentrations of study drug after first dose and at steady state and, if possible, develop a population PK model

## 2.3 Endpoints

### 2.3.1 Primary Endpoint

Proportion of subjects who have died or progressed to RF as defined by progressing to the need for high-flow nasal cannula O2 delivery, noninvasive positive pressure ventilation, invasive mechanical ventilation, or extracorporeal membrane oxygenation (ECMO) therapy at Day 28.

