**Table 2: World Health Organization Ordinal Scale for COVID-19**

Patient State	Description	Score
Uninfected	No clinical or virological evidence of infection	0
Ambulatory	No limitation of activities	1
	Limitation of activities	2
Hospitalized, Mild Disease	Hospitalized, no oxygen therapy	3
	Oxygen by mask or nasal prongs	4
Hospitalized, Severe Disease	Noninvasive ventilation or high-flow oxygen	5
	Intubation and mechanical ventilation	6
	Ventilation + additional organ support – pressors, RRT, ECMO	7
Dead	Death	8

Abbreviations: ECMO = extracorporeal membrane oxygenation; RRT = renal replacement therapy

6. Proportion of patients who develop critical COVID-19 illness as defined by at least one of the following:
  - A. RF defined based on resource utilization requiring at least one of the following: Endotracheal intubation and mechanical ventilation, oxygen delivered by high-flow nasal cannula (heated, humidified, oxygen delivered via reinforced nasal cannula at flow rates > 20 L/min with fraction of delivered oxygen  $\geq 0.5$ ), noninvasive positive pressure ventilation, ECMO, clinical diagnosis respiratory failure (i.e., clinical need for one of the preceding therapies, but preceding therapies not able to be administered in setting of resource limitation)
  - B. Hemodynamic compromise (defined by systolic blood pressure < 90 mm Hg, or diastolic blood pressure < 60 mm Hg or requiring vasopressors)
  - C. Multi-organ dysfunction/failure
7. Time to clinical improvement from baseline value (defined by time to  $\geq 1$ -point improvement on the WHO Ordinal Scale for COVID-19 score – must be maintained through Day 28)
8. Mean change from baseline in WHO Ordinal Scale for COVID-19 score at Day 14/EOT, Day 28, Day 57
9. Incidence and duration of intubation
10. Length of intensive care unit stay
11. Incidence and duration of supplemental O2 administration
12. Incidence and duration of noninvasive ventilation or high-flow nasal cannula O2 administration
13. Incidence and duration of mechanical ventilation
14. Incidence and duration of mechanical ventilation plus additional organ support using vasopressors, and/or renal replacement therapy and/or ECMO
15. Daily ratio of oxygen saturation (SpO2) to fractional inspired O2 (SpO2/FiO2)
16. Length of hospital stay
17. Incidence of re-hospitalization through Day 57
18. Proportion of subjects requiring intensive care unit admission post randomization

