### 4.2 Inclusion Criteria

The subject will be considered eligible for the study after meeting all of the criteria below.

1. Ability to voluntarily provide informed consent that is documented per local requirements
2. An understanding, ability, and willingness to fully comply with study procedures and restrictions
3. Hospitalized subjects with a confirmed SARS-CoV-2 infection
4. Laboratory (polymerase chain reaction [PCR]) confirmed infection with SARS-CoV-2
5. Age  $\geq$  50 years
6. COVID-19 illness of any duration, and O2 saturation measurements  $\leq$  94% over 5 minutes on room air (Note: low flow O2 is permitted, but room air O2 saturation must be  $\leq$  94%)
7. Not with evidence of critical COVID-19 illness as defined by at least one of the following:
  - a. RF defined by requiring at least one of the following:
    - Endotracheal intubation and mechanical ventilation
    - O2 delivered by high-flow nasal cannula at flow rates > 20 L/min with fraction of delivered O2  $\geq$  0.5)
    - Noninvasive positive pressure ventilation (NIPPV)
    - Extracorporeal membrane oxygenation (ECMO)
    - Clinical diagnosis of RF (i.e., clinical need for one of the preceding therapies, but preceding therapies are not able to be administered in setting of resource limitation)
  - b. Hemodynamic compromise (defined by systolic blood pressure < 90 mm Hg, or diastolic blood pressure < 60 mm Hg) or requiring vasopressors
  - c. Multi-organ dysfunction/failure
8. Female subjects of childbearing potential must have a negative pregnancy test at screening or pre-treatment on Day 1

**Note:** Female subjects of childbearing potential are defined as pre-menopausal, < 12 months of amenorrhea post-menopause, or no history of surgical sterilization (hysterectomy or oophorectomy) or tubal ligation.

9. Male and female subjects of childbearing potential must agree to use methods of contraception that are consistent with local regulations for those participating in clinical studies

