### 7.2.6 O2 Saturation/FiO2

The O2 saturation/FiO2 ratio will be collected on the study days as specified in [Table 1](#).

Oxygen saturation will be documented as a representative value at approximately the same time daily and will use a finger pulse oximeter to approximate O2 saturation.

FiO2 values will be obtained at the corresponding time to the O2 saturation values daily. If a subject is receiving supplemental O2 using a device that reports FiO2 values, then the FiO2 value will be reported from the device and recorded in the CRF. However, if there is no FiO2 readout available (e.g., subject is receiving supplemental O2 by nasal prongs), the site will record the method of O2 delivery and the flow rate in liters of O2 per minute (L/min) in the CRF. If the subject is breathing room air, this will be captured in the CRF rather than the O2 delivery flow rate. Note: High Flow Oxygen will only be documented when using a high flow oxygen delivery device that warms and humidifies the oxygen.

The Sponsor will derive the O2 saturation/FiO2 ratio, using accepted standards for converting O2 delivery rates to FiO2 values.

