2.3 Study Endpoints and Evaluations

Primary Endpoint

- Proportion of patients who have died or progressed to RF as defined by progressing to the need for high-flow nasal cannula O₂ delivery, noninvasive positive pressure ventilation, invasive mechanical ventilation, or extracorporeal membrane oxygenation (ECMO) therapy by Day 28.

Secondary Endpoints

1. Safety as assessed by AEs as measured by the Common Terminology Criteria for Adverse Events (CTCAE) v 5.0
2. Proportion of patients surviving [Time Frame: at Day 14, at Day 28, at Day 57]
3. Proportion of subjects who survive without progression to RF [Time Frame: at Day 14, at Day 28, at Day 57]

QMS Document Name: Statistical Analysis Plan	Page 9 of 27
QMS No (include version ref): STF-015-GL.02	Document date: 09JUL2019
CONFIDENTIAL	

4. Time to two successive negative viral titers in nasopharyngeal swab
5. Time to clinical worsening from baseline value (defined by time to ≥ 1 -point worsening on WHO Ordinal Scale for COVID-19):

World Health Organization Ordinal Scale for COVID-19

Patient State	Description	Score
Uninfected	No clinical or virological evidence of infection	0
Ambulatory	No limitation of activities	1
	Limitation of activities	2
Hospitalized, Mild Disease	Hospitalized, no oxygen therapy	3
	Oxygen by mask or nasal prongs	4
Hospitalized, Severe Disease	Noninvasive ventilation or high-flow oxygen	5
	Intubation and mechanical ventilation	6
	Ventilation + additional organ support – pressors, RRT, ECMO	7
Dead	Death	8

Abbreviations: ECMO = extracorporeal membrane oxygenation; RRT = renal replacement therapy

6. Proportion of patients who develop critical COVID-19 illness as defined by at least one the following:
 - A. Respiratory failure defined based on resource utilization requiring at least one of the following: Endotracheal intubation and mechanical ventilation, oxygen delivered by high-flow nasal cannula (heated, humidified, oxygen delivered via reinforced nasal cannula at flow rates > 20 L/min with fraction of delivered oxygen ≥ 0.5), noninvasive positive pressure ventilation, ECMO clinical diagnosis respiratory failure (i.e., clinical need for one of the preceding therapies, but preceding therapies not able to be administered in setting of resource limitation)
 - B. Hemodynamic compromise (defined by systolic blood pressure < 90 mm Hg, or diastolic blood pressure < 60 mm Hg or requiring vasopressors)
 - C. Multi-organ dysfunction/failure

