4.3 Subgroups

The following sub-groups will be examined for the primary endpoint. Results will be displayed in both tabular form. Subgroup analyses are exploratory.

- Age (50 to < 75 vs \geq 75)
- Gender (male vs female)
- previous COVID-19 therapy (yes vs no)
- Regions (North America vs South America)
- Baseline WHO ordinal clinical scale (3 or 4)

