If more than 5% of subjects have insufficient data to confirm RF-free and alive at Day 28, BioAge will employ a MI strategy (SAS MI, MIANALYZE) with missing at random (MAR) based protocol stratification factors (age and region), treatment, and the discharge status prior to or on Day 28. Following steps will be followed for multiple imputation.

Step 1: which will be carried out to produce n (exp. 25) imputed datasets

The SAS procedure PROC MI using the FCS (fully conditional specification method) statement with LOGISTIC imputation method to impute RF28 assuming no covariate will be missing.

One must also specify a VAR statement with outcome variable being the last in the order. If any covariate is expected to have missing and need to be imputed as well

`"LOGISTIC (RF28SUB_MI=TRT01P REGION AGEGRN DISC28)"` also need to be added after the FCS statement.

```
PROC MI DATA=RF28 _ DATA SEED=1305417 NIMPUTE=25 OUT=OUTLOG;  
  CLASS RF28 TRT01P REGION AGEGRN DISC28;  
  VAR TRT01P REGION AGEGRN DISC28 RF28;  
  FCS LOGISTIC (RF28SUB_MI=TRT01P REGION AGEGRN DISC28) ;  
RUN;
```

Where:

RF28 is respiratory failure or death prior to or on Day 28

TRT01P is randomized treatment (Placebo/Asapiprant)

REGION: region of patient's location (North America/South America)

AGEGRN: age group (50 - <75, >=75)

DISC28: discharge status prior to or on Day 28

Step 2: Each of 25 complete data set will be analyzed using standard logistic analyses as specified for primary efficacy analysis in SAP, i.e. PROC LOGISTIC will be used for RF28 with predefined covariates (region and age group) and treatment group.

```
PROC LOGISTIC DATA=OUTLOG ;  
  CLASS RF28 TRT01P REGION AGEGRN ;  
  MODEL RF28=TRT01P REGION AGEGRN / COVB;  
  BY IMPUTATION ;  
  ODS OUTPUT PARAMETERESTIMATES=LGSPARMS;  
RUN;
```

Step 3: The results logistic regression from the 25 complete data sets are combined for the parameter inference (i.e. coefficient estimate, 95% confidence interval, and p-value) using PROC MIANALYZE

```
PROC MIANALYZE PARMs=LGSPARMS;  
  MODELEFFECTS INTERCEPT TRT01P REGION AGEGRN;  
RUN;
```

QMS Document Name: Statistical Analysis Plan	Page 19 of 27
QMS No (include version ref): STF-015-GL02	Document date: 09JUL2019
CONFIDENTIAL	

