10.2.1 Proportion of binary endpoints

The number and percentage of the following binary endpoints will be presented by treatment and timepoint. Comparison of proportion of patients between treatment at each timepoint will be analysed by the same manner as primary endpoint.

- Proportion of patients who had survived at each timepoint at Day 14, at Day 28, at Day 57: which is defined as patients who had no documented death prior or on timepoint at Day 14, 28, 57.
- Proportion of patients who survive without progression to RF at each timepoint at Day 14, Day 28, Day 57: which is defined as patients who had neither documented death nor respiratory failure prior or on timepoint at Day 14, 28, 57.
- Proportion of patients who had intubation during the study: which will be defined as proportion of patients who had any documented intubation during the study.
- Proportion of patients who develop critical COVID-19 illness as defined by at least one the following:
 - A. Respiratory failure defined based on resource utilization requiring at least one of the following: Endotracheal intubation and mechanical ventilation, oxygen delivered by high-flow nasal cannula (heated, humidified, oxygen delivered via reinforced nasal cannula at flow rates > 20 L/min with fraction of delivered oxygen ≥ 0.5), noninvasive positive pressure ventilation, ECMO clinical diagnosis respiratory failure (i.e., clinical need for one of the preceding therapies, but preceding therapies not able to be administered in setting of resource limitation)
 - B. Hemodynamic compromise (defined by systolic blood pressure < 90 mm Hg, or diastolic blood pressure < 60 mm Hg or requiring vasopressors)
 - C. Multi-organ dysfunction/failure
- Proportion of patients requiring intensive care unit admission: which is defined as patients who had been admitted to intensive care unit during the study.
- Incidence of supplemental O₂ administration: which will be defined as proportion of patients who had any documented post-dosing supplemental O₂ administration during the study.
- Incidence of noninvasive ventilation or high-flow nasal cannula O₂ administration: which will be defined as proportion of patients who had any documented post-dosing noninvasive ventilation or high-flow nasal cannula O₂ administration.
- Incidence of mechanical ventilation: which will be defined as proportion of patients who had any documented post-dosing mechanical ventilation.

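### Do the two wordings of respiratory failure leave the primary endpoint undefined?

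*Protocol*

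**What the plan says.** **Primary endpoint.** Protocol 2.3.1 reads "Proportion of subjects who have died or progressed to RF as defined by progressing to the need for high-flow nasal cannula" oxygen, noninvasive positive pressure ventilation, invasive ventilation or ECMO. SAP 2.3 repeats it: "Proportion of patients who have died or progressed to RF as defined by progressing to the need for high-flow nasal cannula" and the same list. Neither gives a flow rate or oxygen fraction.

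**Eligibility.** Protocol 4.2, criterion 7a, excludes subjects already in RF. It counts oxygen "delivered by high-flow nasal cannula at flow rates > 20 L/min with fraction of delivered" oxygen at or above 0.5. It also counts a clinical diagnosis of RF where the therapy is needed but resources do not allow it.

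**Critical illness.** Secondary endpoint 6A (Protocol 2.3.2, SAP 2.3 and SAP 10.2.1) uses the same limit, for heated and humidified oxygen by "reinforced nasal cannula at flow rates > 20 L/min with fraction of delivered oxygen" at or above 0.5, and the same resource-limitation item.

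**Analysis variables.** The note under the multiple-imputation code in SAP 10.1 says "RF28 is respiratory failure or death prior to or on Day 28". SAP 10.2.1 defines secondary endpoint 3 as "patients who had neither documented death nor respiratory failure prior or on timepoint at Day 14, 28, 57".

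**Data capture.** Protocol 7.2.6: "High Flow Oxygen will only be documented when using a high flow oxygen delivery device that warms and humidifies the oxygen".

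**Baseline state.** Inclusion criterion 6 names low-flow oxygen as permitted. The SAP 4.3 subgroup is "Baseline WHO ordinal clinical scale (3 or 4"). High-flow oxygen is score 5 on that scale.

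**The concern.** One term, RF, carries two descriptions in one protocol. Two gaps seem to follow.

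- **At entry.** A subject on high flow below the 7a limit passes 7a as not in RF. Under the unrestricted primary wording, that subject may already be in the state that counts as an event. If RF28 is read literally, the subject is a failure from Day 1. If progression is required, the high-flow component cannot be reached.
- **After baseline.** A subject who starts high flow below the limit is a primary failure but has no RF under 6A. The two RF counts in one report could then differ without a stated reason, and secondary endpoint 3 does not say which description it uses.

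At stake would be a primary event that depends on an unwritten programming choice, with some loss of power.

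**Working it through.** **1. The plan's own figure.** Inputs from Protocol 8.6: 31% and 15%, two-sided 5%, 90% power, 1:1, Fisher's exact test. The mean rate is 0.23.

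- Uncorrected n per arm = [1.960·√(2·0.23·0.77) + 1.2816·√(0.31·0.69 + 0.15·0.85)]² / 0.16² = (1.1665 + 0.7488)² / 0.0256 = 143.3, so 144 (288 in total).
- With continuity correction: (143.3/4)·[1 + √(1 + 4/(143.3·0.16))]² = 155.5, so 156 (312 in total).

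The stated 312 reproduces. Exact Fisher power at 156 per arm is 90.5%.

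**2. The entry gap.** Let x be the share of subjects on high flow below the limit at entry. The documents do not give x, so 1% to 10% is assumed. The other subjects have 31% and 15%.

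- Scored as events: rates x + (1−x)·0.31 and x + (1−x)·0.15.
- No events at all: rates (1−x)·0.31 and (1−x)·0.15.
- The risk difference is (1−x)·16 points under both.

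| x | Difference (points) | Power, scored as events | Power, no events |
|---|---|---|---|
| 0 | 16.0 | 90.5% | 90.5% |
| 1% | 15.8 | 89.2% | 90.1% |
| 2% | 15.7 | 87.9% | 89.7% |
| 5% | 15.2 | 83.5% | 88.4% |
| 10% | 14.4 | 75.4% | 86.0% |

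At 1% the two readings differ by 0.9 points of power, and at 2% by 1.8. The last column is an extreme, because death and intubation would still count. Support in use before randomization is unrelated to the assigned arm, so neither reading favours a treatment; it only dilutes the contrast.

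**3. Which x is plausible?** Inclusion 6 names low-flow oxygen. Protocol 8.4 and SAP 4.3 foresee only baseline scores 3 and 4. By its addendum, SAP version 5.0 was written after enrollment had stopped and after a blinded review that looked at RF by baseline score. It still lists only 3 and 4 and reports separation only at score 3. Had score-5 subjects been present and scored as events from Day 1, score 5 would have shown separation too. This points to x at or near zero, without proving it.

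**4. Is the primary event undefined?** The definition stands in Protocol 2.3.1 and SAP 2.3, and both speak of progressing. The RF28 line is a variable label beside imputation code that runs only if more than 5% of subjects lack the outcome. It abbreviates the endpoint and does not compete with it. Protocol 7.2.6 supplies the working meaning of high flow: a device that warms and humidifies.

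**5. The gap after baseline.** Critical illness is a different endpoint with a different name, a composite that also includes hemodynamic compromise and organ failure, and its RF component is spelled out. Secondary endpoint 3 follows directly after the primary endpoint in the protocol and uses its language of progression, so the natural reading is the primary list.

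**The case for a change.** The strongest case concerns high flow started after baseline, since that needs no unusual enrollment. The SAP says that it prevails over the protocol, yet SAP 10.1 speaks only of progression to RF, and the one place in SAP section 10 that spells RF out is the thresholded list under critical illness. A programmer might take that list for the primary variable. Suppose 31% and 15% describe the unrestricted endpoint, and a share of events in each arm is high flow below the limit only. Fisher power at 156 per arm under the thresholded list would then be 88.4%, 86.0%, 80.1% or 72.9% for assumed shares of 5%, 10%, 20% or 30%. The version 2.0 entry in the change log also suggests that one definition was intended.

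The inconsistency stands. The loss of power does not follow, because those figures require the analyst to replace the endpoint defined in SAP 2.3 with a component of another endpoint. The shares are assumed, and the planned size may not have been reached: the SAP addendum says enrollment stopped before the interim analysis, which was set at about 208 subjects.

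Two smaller points are fair. SAP 4.7 lets the earliest score on the day of randomization serve as baseline if none was taken before it, so high flow begun that day could appear as a baseline score of 5. That affects the baseline label; high flow started after randomization still meets the primary definition. The resource-limitation item is absent from the primary list, but the primary wording turns on need, which leaves room for such a subject.

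**Conclusion.** The concern is right about the wording and does not call for a change to the plan. The passages use RF in two ways, and a reader comparing the primary RF count with the RF part of critical illness should know that the lists differ. Followed as written, the plan still gives a sound primary result: its event list is explicit, it counts progression, and capture of high flow is tied to a type of device. What is missing is derivation detail that analysts would fill sensibly by treating support already in use before randomization as the starting state.

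At an entry share of 1% to 2%, power lies between 87.9% and 90.1%, against 90.5% at the planned size. An extra analysis excluding subjects with a baseline score of 5 or more would act on a group that is probably empty.

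This rests on two assumptions: that few or no subjects entered on high flow, which the documents support but do not state, and that the primary variable is built from the list in SAP 2.3. No view is taken on which oxygen limit is clinically right.
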